## 10.2 Calendar

Study Days	Pre-Study	Cycles 1-4 Day 1	Cycles 1-4 Day 8	Cycles 4+ Days 1 and 8	30 Day Follow Up	Long term Follow-Up
REQUIRED ASSESSMENTS						
Informed Consent	X					
Demographics	X					
Medical History	X					
Height	X					
Weight	X	X		X c	X	X
Vitals (blood pressure, pulse, temperature, and respiratory rate)	X	X	X	X	X	X
Physical Examination	X	X		X c	X	X
Concomitant Medication Assessment	X	X	X	X c	X	X
Karnofksy PS	X	X	X	X	X	X
Baseline Symptoms	X	X f				
Adverse Event Assessment		X	X	X	X	X
CBC / diff / platelets/ b	X	X b	X b	X b	X	X
Serum Chemistry a,b	X	X b	X b	X b	X	X
PT/INR	X					
β-HCG, women of childbearing potential	X					
EKG	X					
DISEASE ASSESSMENT						
MRI brain with and without contrast	X			X d		
CT chest, abdomen and pelvis with IV contrast or total body FDG PET	X			X e		
TREATMENT						
Eribulin mesylate		X	X	X		

**a:** Albumin, alkaline phosphatase, total bilirubin, bicarbonate, BUN, calcium, chloride, creatinine, glucose, potassium, total protein, SGOT [AST], SGPT [ALT], sodium, Mg. Calculated creatinine clearance will be done if creatinine and/or BUN are abnormal.

**b:** Laboratory Studies: to be completed 0-3 days prior to eribulin administration

**c:** Day 1 only

**d:** MRI brain to be completed every 12 weeks while on study eribulin mesylate

**e:** CT chest/abd/pelvis or total body PET every 12 weeks in patients with systemic disease while on study eribulin mesylate.

**f:** cycle 1 day 1 only

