### **11.1 Antitumor Effect – CNS Metastases**

Patients will have a baseline MRI brain scan (within 30 days before initiation of therapy) and should be re-evaluated for response by MRI scan after 12 weeks of starting the study.

Response and progression by MR will be evaluated in this study using WHO/modified McDonald's criteria.

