#### **11.1.2 Disease Parameters**

Measurable Disease Measurable lesions are defined as brain lesions that can be accurately measured in at least one dimension) as  $\geq 10$  mm by Gd-MRI. All tumor measurements must be recorded in millimeters.

Note: Tumor lesions that are previously treated with stereotactic radiosurgery are not allowed as target lesion.

Non-measurable disease All other lesions including small lesions (longest diameter  $< 10$  mm are considered non-measurable disease.

Note: Cystic lesions that meet the criteria for radiographically defined simple cysts should not be considered as malignant lesions (neither measurable nor non-measurable) since they are, by definition, simple cysts.

‘Cystic lesions’ thought to represent cystic metastases can be considered as measurable lesions if they meet the definition of measurability described above. However, if non-cystic lesions are present in the same patient, these are preferred for selection as target lesions.

Target lesions: All measurable brain metastases  $\geq 10$  mm should be identified as target lesions and recorded and measured at baseline. Target lesions should be selected on the basis of their size (lesions with the longest diameter but in addition should be those that lend themselves to reproducible repeated measurements. It may be the case that, on occasion, the largest lesion does not lend itself to reproducible measurement in which circumstance, the next largest lesion which can be measured reproducible should be selected. A sum of the diameters for all target lesions will be calculated and reported as the baseline sum diameters.

Non-target lesions: All other lesions should be identified as non-target lesions and should also be recorded at baseline. Measurements of these lesions are not required, but the presence, absence, or in rare cases unequivocal progression of each should be noted throughout follow-up.

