#### 11.1.4 Response Criteria

##### Measurement of Response

Gadolinium-enhanced brain MRI will be checked at baseline, 12 weeks after starting treatment, and every 12 weeks thereafter until progression. The slice thickness of MRI should be less than 5 mm throughout the brain (2 to 3 mm thickness is highly recommended). MR imaging will be collected electronically for ad hoc central review of responses.

Response in the brain also will be measured using dimensional measurements (WHO/modified McDonald's criteria). Systemic responses will be assessed using the revised Response Evaluation Criteria in Solid Tumors (RECIST) guideline (version 1.1) (Eisenhauer 2009).

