##### **Time to CNS Progression**

Patients will be followed clinically and radiographically. The date at which the tumor is documented to have first enlarged (brain or systemic progression) by 25% from best response (steroid dose stable or increased, neurologically stable or worse) will be considered the date of tumor progression. Time to progression will be the interval between the date of study entry and the date of tumor progression. In the event of a discrepancy and for the purposes of analysis, the treating physician's date of tumor progression will be deemed to be correct. Tissue confirmation of CNS tumor progression by stereotactic biopsy or other surgical procedure is encouraged to rule out treatment effect as a cause of radiographic worsening. Ancillary imaging techniques such as PET imaging, perfusion MRI, or MR spectroscopy of all "recurrent" or "progressive" lesions of CNS is recommended for patients at centers with access to these technologies.

Responses in the CNS and systemic compartments will be assessed by the same criteria in order to avoid confusion in the conduct of the trial. CNS disease will be imaged by MRI with gadolinium, and systemic disease will be imaged by CT scan with IV contrast.

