### **Sample size and study duration**

Clinically, in this population of breast cancer with brain metastases, we expect that a therapy would induce a 35% 3-month PFS rate. A 15% rate would not be considered meaningful, and thus anything statistically significant > 15% would be considered a positive study. The 3-month CNS PFS of 35% as an indicator of efficacy was based on studies of chemotherapy in brain metastases, which demonstrated 3-month CNS PFS rates in the range of 22%–50% (34-36). If 8 or more patients (out of 20) remain progression free at three months this will be taken as evidence that eribulin may have a positive impact on PFS, as the estimate of the proportion of patients with PFS would be 40%, and the 95% CI would be 18.5-61.5%, which does not include 15%. Thus, we have determined that a total of 20 evaluable patients will be required for the study.

In terms of availability of patients to enroll in this study, the proposed institution for this trial is the Case Comprehensive Cancer Center, a collaboration that includes clinical research activities at both University Hospitals Siedman Cancer Center and the Cleveland Clinic Foundation.

Approximately 9000 new cancer patients are seen at Case Comprehensive Cancer Center annually of which 30-40 patients have brain metastases from metastatic breast cancer in Seidman network

alone. The anticipated accrual rate is 20 patients per year. We have the predefined response on eribulin mesylate which will be assessed by CNS RECIST 1.1 criteria using MRI scan.

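### The plan names two different criteria for CNS disease and writes the CNS progression event in several ways, while the success rule turns on 8 versus 7 of 20 patients

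*Combined protocol and SAP*

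**What the plan says.** **Criterion.** Section 11.1 sets the general rule for the brain: "Response and progression by MR will be evaluated in this study using WHO/modified McDonald" criteria. Section 11.1.4 (Measurement of Response) and the table in 11.1.4.1 repeat it. For disease outside the brain, Section 11.1.4 says "Systemic responses will be assessed using the revised Response Evaluation Criteria in Solid Tumors (RECIST) guideline (version 1.1"), and Section 11.2 agrees. Two statements do not fit:

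- Section 13.0 (Sample size and study duration), which also holds the 8-of-20 rule, says "We have the predefined response on eribulin mesylate which will be assessed by CNS RECIST 1.1 criteria using MRI scan". CNS RECIST 1.1 appears nowhere else and is not defined.
- Section 11.1.4 (Time to CNS Progression) says "Responses in the CNS and systemic compartments will be assessed by the same criteria in order to avoid confusion".

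**Event.** Time to CNS Progression dates progression from when the tumor "first enlarged (brain or systemic progression) by 25% from best response (steroid dose stable or increased, neurologically stable or worse"). The definition of CNS response later in 11.1.4 and the table in 11.1.4.1 each give a different rule, set side by side under the working.

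**Lesions.** Section 11.1.2 makes every brain lesion of at least 10 mm a target and adds: "A sum of the diameters for all target lesions will be calculated and reported as the baseline sum diameters". The table in 11.1.4.1 works with at most two targets and, in its partial-response row, with products of perpendicular diameters.

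**Analysis.** Section 13.1 takes the proportion of patients without CNS progression at 3 months and does not point to any of these definitions.

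**The concern.** The primary result is a count, so it depends on what makes a patient an event. The statistical section names one criterion and the measurement section another. Within the measurement section, the event changes from one subsection to the next.

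The week-12 visit is where this matters. Notes d and e to the Section 10.2 calendar put brain MRI and body imaging on the same interval ("CT chest/abd/pelvis or total body PET every 12 weeks in patients with systemic disease while on study eribulin mesylate"), so a stable brain with growing systemic disease can appear at the primary read itself. The trial has a single arm, and independent reading is optional: "MR imaging will be collected electronically for ad hoc central review of responses". Two people applying the protocol in good faith could reach different counts from the same scans and notes.

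**Working it through.** **1. The plan's own figure.** Inputs from Section 13.0: n = 20, success at 8 or more, reference rate 15%. The Wald interval is p ± 1.96·√(p(1−p)/n).

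- 8/20: 0.40 ± 1.96·√(0.40·0.60/20) = 0.40 ± 0.215, giving 18.5–61.5%. This matches the plan and excludes 15%.
- 7/20: 0.35 ± 1.96·√(0.35·0.65/20) = 0.35 ± 0.209, giving 14.1–55.9%. This includes 15%.

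One patient separates the two verdicts.

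**2. The progression wordings side by side.**

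| Place | Size rule | Steroids | Other events |
|---|---|---|---|
| 11.1.4, Time to CNS Progression | 25% enlargement from best response, no unit; brain or systemic | stable or increased | none listed |
| 11.1.4, Definition of CNS response | more than 25% in area | no decrease since the last evaluation; the steroid sentence that follows is tied to the two months after radiotherapy | none listed, but a note allows progression without growth in exceptional circumstances |
| 11.1.4.1, table | at least 25% in up to two targets, against nadir | no proviso on decrease in the extracted text | new CNS lesion, unequivocal progression, tumor-related steroid increase, new or worse tumor-related neurologic symptoms |

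Best response and nadir both equal baseline at the first scheduled read, so that difference has no effect there.

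**3. One week-12 visit, two answers.**

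- *Brain stable, systemic disease up 25%.* An event on the wording of Time to CNS Progression; not an event under the other two.
- *20×20 mm to 25×20 mm.* 500/400 = 1.25, exactly 25% in area. An event under the table if its progression row uses area; not an event where more than 25% is required.
- *Tumor-related steroid increase, or worse symptoms, alone.* An event under the table. Not listed in the definition of CNS response, unless called exceptional.
- *20×20 mm to 23×23 mm.* Area: 529/400 = 1.3225, or +32%, above 25%. Diameter: 23/20 = 1.15, or +15% and +3 mm. If CNS RECIST 1.1 means the Section 11.2.3 thresholds (at least 20% and at least 5 mm), this is not progression. That reading is an assumption, since the term is undefined.

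**4. Provisional conflicts.** The table in 11.1.4.1 carries reference marks whose notes are missing from the extracted text. They could settle the number of lesions, the metric for progression and the handling of a steroid decrease. As an illustration of lesion number, take round lesions of 22, 20, 15 and 15 mm growing to 25, 23, 15 and 15 mm:

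- Two largest, products: (625 + 529)/(484 + 400) = 1154/884 = 1.305, or +30.5%.
- All four, products: (1154 + 450)/(884 + 450) = 1604/1334 = 1.202, or +20.2%.

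The first passes 25% and the second does not.

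**5. How near the margin the count may fall.** Binomial with n = 20. At the plan's expected 35%, P(7) = 0.184 and P(8) = 0.161, together 34.6%. The same sum is 11.2% at 22% and 19.4% at 50% (the ends of the plan's cited range), and 2.1% at 15%.

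**The case against.** **The Section 13.0 sentence speaks of response, closes an accrual paragraph, and stands alone against three consistent statements in Section 11.** This is fair: it looks like a stray label. A reader might infer that the primary analysis will be run by RECIST, and the documents do not support that. But Section 11.0 itself calls the primary endpoint response in the brain, so the sentence cannot be dismissed as irrelevant. The inconsistency within Section 11.1 does not depend on it.

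**The endpoint is CNS-only.** Sections 2.1, 13.0 and 13.1 all say so, and Section 3.4 lists systemic and CNS progression separately. A reader might infer that systemic progression will be counted in the primary endpoint; that is a strained reading. The words still stand under the heading Time to CNS Progression.

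**New brain lesions are covered.** A 20×20 mm lesion unchanged plus a new 6×6 mm lesion adds only 9% in area (436/400). However, the 11.1.4.1 table and the best-response table both count a new lesion, and the exceptional-circumstances note leaves room for it. This is an omission in one place, not an opposite rule.

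**Section 11.1.2 is not a further progression rule.** Its sum of diameters is a baseline item with no threshold, so a reader should not set it against the 25% as a competing test.

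**The physician's date prevails in a discrepancy, and progression ends treatment, so the call is made during care.** This limits later choice. A reader might infer that the definition will be picked once results are known; the documents do not show that. The clause settles a date, however, and supplies no criterion.

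**The margin depends on the interval.** The exact 95% interval for 7/20 is 15.4–59.2%, which excludes 15%; for 6/20 it is 11.9–54.3%, which includes it. That moves the margin by one patient but does not remove it.

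**Conclusion.** The point holds. An undefined criterion is named in the section that carries the success rule, the shared-criteria sentence contradicts the assignment of RECIST 1.1 to systemic disease, and the CNS progression event is not written consistently. Conflicts over lesion number, progression metric and steroid decrease remain provisional until the table's notes are seen. The 20×20 to 23×23 mm example rests on the stated assumption about CNS RECIST 1.1, and the exact-25% example on area being the table's metric.

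The consequence is that one patient classified differently at the margin changes the verdict under the plan's own interval. A reader might take 34.6% as the chance of that. It is only the chance of a count of 7 or 8 at a true rate of 35%, and each count flips in one direction only (8 to 7, 16.1%; 7 to 8, 18.4%). How often patients would be classified differently cannot be estimated from the documents. The plan's sample-size interval is not in error on this point.

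**What to change.** 1. Section 13.0: replace CNS RECIST 1.1 with the WHO/modified McDonald criteria already named in Sections 11.1, 11.1.4 and 11.1.4.1.
2. Section 11.1.4, Time to CNS Progression: replace the shared-criteria sentence with WHO/modified McDonald for the CNS and RECIST 1.1 for systemic disease. Restrict the CNS PFS event to CNS progression, in line with Sections 2.1, 13.0 and 13.1. This concerns the endpoint only and leaves the treatment-stopping list in Section 3.4 unchanged; systemic disease keeps its own objective, 2.2.4.
3. Check the notes to the 11.1.4.1 table in the source file. Then reconcile Sections 11.1.2, 11.1.4 and 11.1.4.1 to one CNS progression definition for the primary analysis: number of target lesions, metric, threshold and reference scan, steroid handling, and the list of events not based on measurement. Which event list should govern is for the investigators to settle; it is not proposed here.
4. Section 13.1: cite that definition.

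Do this before the week-12 reads are analysed. The cost is wording changes and possibly a second diameter per target lesion on scans already taken, with no added patients or scans.

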### **Evaluability**

To be evaluable for inclusion in the primary objective and secondary objectives, patients must have baseline and week 12 MRI.

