## **3.0 STUDY DESIGN**

### **3.1 Design:**

This is a phase II study that will require 20 patients to evaluate the primary objective (CNS PFS at 3 months). Study patients will have a baseline brain MRI and a second MRI at 12 weeks to evaluate disease.

**3.2 Number of Subjects:** A total of 20 evaluable patients will be required for the study:

**3.3 Expected Duration of Subject Participation:** Death or disease progression or toxicity.

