### **3.6 Replacement of Subjects**

Subjects who do not obtain the two MRI scans (baseline and 12 weeks) will be considered not evaluable for response and will be replaced.

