#### **11.1.1 Definitions**

Evaluable for toxicity All patients will be evaluable for toxicity from the time of registration to protocol.

Evaluable for objective response Only those patients who have measurable disease present at baseline, have received eribulin as per the protocol, and have had their disease re-evaluated will be considered evaluable for response. These patients will have their response classified according to the definitions stated below. (Note: Patients who exhibit objective disease progression prior to the end of cycle 1 will also be considered evaluable.)

Evaluable Non-Target Disease Response Patients who have lesions present at baseline that are evaluable, but do not meet the definitions of measurable disease, have received at least one cycle of therapy, and have had their disease re-evaluated will be considered evaluable for non-target disease. The response assessment is based on the presence, absence, or unequivocal progression of the lesions.

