#### 11.1.4.1 Evaluation of Target lesions by MRI using McDonalds criteria

Response	WHO/modified McDonald Criteria
CR (complete response)	Complete disappearance of all enhancing disease and off all steroids
PR (partial response)	<math>\geq 50\%</math> reduction in the sum of products of the perpendicular diameters of up to 2 target lesions* plus no new lesion, no progression of non-measurable CNS lesion, no increasing steroid requirements, and no worsening of neurologic symptoms
SD (stable disease)	$< 50\%$ reduction in size or $< 25\%$ increase in size.
PD † (progressive disease)	
 
• <math>\geq 25\%</math> increase of up to 2 target CNS lesions relative to nadir
 
• New CNS lesions
 
• unequivocal progression (defined below‡)
 
• Tumor-related increase in steroid dose
 
• New or worsening tumor-related neurologic symptoms
 

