### **13.1 Methods to address the study objectives**

#### **Primary Objective:** CNS PFS at 3 months

We will assess the proportion of subjects without CNS progression at 3 months. We hypothesize that this will be at least 35%. We will generate a Kaplan-Meier curve of CNS PFS and estimate the PFS and 95% CI of the PFS.

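### Every patient without a week-12 MRI is dropped from the primary analysis and replaced, even after death or clinical CNS progression, so 3-month CNS PFS is biased upward to the extent that unscanned patients do worse

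*Combined protocol and SAP*

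**What the plan says.** The population for the primary analysis is set in two places. Section 13.0, Evaluability: "To be evaluable for inclusion in the primary objective and secondary objectives, patients must have baseline and week 12 MRI". Section 3.6: "Subjects who do not obtain the two MRI scans (baseline and 12 weeks) will be considered not evaluable for response and will be replaced". The sample size paragraph of section 13.0 asks for 20 evaluable patients and calls the study positive if 8 or more of the 20 are progression free at three months.

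The endpoint is described without a death component. Section 13.1, primary objective: "We will assess the proportion of subjects without CNS progression at 3 months". Section 11.1.4, Time to CNS Progression: "Time to progression will be the interval between the date of study entry and the date of tumor progression". Despite its title, that paragraph takes progression in either the brain or the body as its event. Death appears in sections 3.3 to 3.5 as an end of participation, treatment or follow-up, and through overall survival, but never as a CNS PFS event.

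The table in section 11.1.4.1 includes progression criteria that need no scan: a tumor-related rise in steroid dose, and "New or worsening tumor-related neurologic symptoms". Section 11.1.1 notes: "Patients who exhibit objective disease progression prior to the end of cycle 1 will also be considered evaluable". That note concerns evaluability for objective response, and the Evaluability paragraph has no matching exception.

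On scan timing, section 3.1 says "Study patients will have a baseline brain MRI and a second MRI at 12 weeks to evaluate disease", and section 11.1 says patients "should be re-evaluated for response by MRI scan after 12 weeks of starting the study". Section 11.1.4 continues MRI until progression. Footnote d of the section 10.2 calendar ties the 12-weekly MRI to being on eribulin, section 3.3 ends participation at death, progression or toxicity, and section 3.4 stops treatment at systemic as well as CNS progression.

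**The concern.** Entry to the primary analysis depends partly on the outcome. A patient who dies in week 6 cannot have the week-12 scan, so she leaves the denominator and another patient takes her place. A patient with clinical CNS progression in week 8 who is never scanned leaves in the same way, although section 11.1.4.1 would call her progressed. If such patients do worse than those who reach the scan, the reported rate is too high, and so is the planned Kaplan-Meier curve if it is drawn on the same set. The stated primary objective is to determine 3-month CNS PFS, so the distortion falls on the quantity the trial exists to estimate.

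The same sentence also governs the secondary objectives. Read literally, it removes early deaths from overall survival (section 13.1, objective 2.2.5) and unscanned patients from toxicity. Sections 11.1.1 and 11.2.1 instead make all patients evaluable for toxicity, from registration and from first treatment respectively.

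**Working it through.** **Inputs from section 13.0.** Rate of no interest 15%, target 35%, 20 evaluable patients, success at 8 or more, stated 95% interval for 8/20 of 18.5-61.5%.

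**1. The plan's own figure.** Wald interval: 0.40 ± 1.96 × √(0.40 × 0.60 / 20) = 0.40 ± 0.215, or 18.5-61.5%. It reproduces. The exact (Clopper-Pearson) interval is 19.1-63.9%. By exact binomial, P(X ≥ 8 | n = 20) is 0.6% at a true 15% and 39.9% at a true 35%.

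**2. Size of the bias.** Let L be the share of treated patients without the week-12 MRI, p the true rate in all treated patients, and r the progression-free rate of the unscanned relative to the scanned. If s is the rate in the scanned, p = (1 − L)s + L·r·s, so s = p / (1 − L + L·r). L is not in the documents; 10-40% is an assumption. Example: p = 35%, L = 20%, r = 0 gives 0.35 / 0.80 = 43.8%.

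| Loss L | 35% reads, r = 0 | 35% reads, r = 0.5 | 15% reads, r = 0 | 15% reads, r = 0.5 |
|---|---|---|---|---|
| 10% | 38.9% | 36.8% | 16.7% | 15.8% |
| 20% | 43.8% | 38.9% | 18.8% | 16.7% |
| 30% | 50.0% | 41.2% | 21.4% | 17.6% |
| 40% | 58.3% | 43.8% | 25.0% | 18.8% |

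With r = 1 there is no bias. The r = 0 columns are an upper bound and treat death as failure.

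**3. Is such a loss plausible?** Section 1.4 cites median survival of 4-7.5 months by subtype. Assuming exponential survival, the share dead by week 12 (84 / 30.44 = 2.76 months) is 1 − 2^(−2.76/median): 38% at 4 months and 23% at 7.5 months. The cited radiosurgery medians of 7-18 months give 24% to 10%. These are other populations, and this trial's eligibility criteria should lower the figures.

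**4. False-positive rate of 8/20 at a true 15%.** Putting the apparent rates from step 2 into P(X ≥ 8 | n = 20):
- r = 0: 1.1%, 2.2%, 4.7% and 10.2% at 10, 20, 30 and 40% loss. It passes 5% above about 31% loss.
- r = 0.5: 0.8%, 1.1%, 1.6% and 2.2%. It passes 5% above about 62% loss.

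**5. Exposure of the conclusion.** Put replaced failures back in the denominator and see when the 95% interval first includes 15%.
- 8 successes, Wald: 8/23 has lower limit 15.3%; 8/24 gives 14.5-52.2%. Four replaced failures suffice.
- 8 successes, exact: 8/24 has lower limit 15.6%; 8/25 has 14.95%. Five are needed.
- 9 successes: eight are needed by Wald (9/28, 14.8%) and ten by the exact method (9/30, 14.7%).

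**The case against.** - **Clinical progression is defined.** A reader might infer that the protocol never treats clinical CNS worsening as progression. That is not so: section 11.1.4.1 lists it, section 11.1.4 follows patients clinically as well as by imaging, and section 11.1.1 keeps some early progressors evaluable for response. What stands is a conflict: sections 3.6 and 13.0 remove such a patient if she lacks the scan.
- **The Evaluability sentence may not be meant literally.** It would strip early deaths out of overall survival, section 3.6 speaks only of response, and a Kaplan-Meier curve has little use if everyone must reach week 12. This is fair, and it means the text does not prove which analysis would be run. But the sentence names the primary objective, and nothing overrides it.
- **Counting death is a choice.** Section 13.1 measures freedom from CNS progression, and a non-CNS death could be treated as a competing event. The endpoint's name supports counting death, but the upper-bound figures depend on that choice.
- **Not every unscanned patient is a failure.** Withdrawal (section 3.4) or claustrophobia in the scanner (section 8.2.1) may have nothing to do with CNS outcome. Eligibility (4.1.5, 4.1.6, 4.1.10, 4.2.2) limits early loss, section 3.4 asks for every effort to complete assessments, and silent progression found at week 12 stays in the denominator. All of this stands, which is why the bias is stated conditionally.
- **The decision rule is conservative.** A reader might infer that a positive result could not be trusted. Steps 4 and 5 do not support that, except at or next to 8 of 20.

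**Conclusion.** The concern holds in conditional form. As written, the plan excludes and replaces every patient without a week-12 MRI, has no exception for death or earlier CNS progression, and never counts death as a CNS PFS event. The estimate is then biased upward to the extent that unscanned patients do worse: by 3.9 to 23.3 percentage points at a true 35% if all of them fail, 1.8 to 8.8 points if they do half as well, and nothing if they do equally well. These sizes rest on an assumed 10-40% loss, and the upper bound also on death counting as failure.

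The harm is mainly to the estimate. The test is exposed only for results at or next to the threshold. Whether patients are scanned after eribulin stops, which affects how many are lost, cannot be settled from the text: sections 3.1, 11.1 and 11.1.4 point one way, and section 3.3 and footnote d the other. This should be corrected before the analysis, because the distorted quantity is the primary endpoint and the repair is mostly wording.

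**What to change.** 1. Make the primary set all eligible patients who receive at least one dose of eribulin. Replace only patients never dosed.
2. Define a CNS PFS event as death from any cause or CNS progression, radiographic or clinical as in section 11.1.4.1, counted as failure whether or not the week-12 MRI exists. State that the brain-or-systemic event in section 11.1.4 does not define this endpoint, or reconcile it explicitly.
3. Limit the Evaluability paragraph so that it does not govern overall survival or toxicity.
4. Censor scans missing for other reasons in the Kaplan-Meier estimate already planned, read after the week-12 window closes (7 days either way, section 10.1.1). Give missing-as-failure and the MRI-evaluable set as sensitivity analyses.
5. Keep the success bar no lower than 8 of 20. A simple count has no place for a censored patient, so the rule needs restating. If it becomes a 95% lower limit above 15%, fix the interval method in advance and state its error rate. At 7/20 the lower limit is 15.4% (exact), 15.7% (log-log Kaplan-Meier) and 14.1% (Wald), so the first two would let 7/20 pass and raise the false-positive rate from 0.6% to 2.2%.
6. Reconcile sections 3.1, 3.3, 3.4, 3.6, 10.2 (footnote d), 11.1, 11.1.1, 11.1.4, 11.1.4.1 and 13.0-13.1, including whether the week-12 MRI is obtained after eribulin stops.

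**Cost.** Mostly protocol wording and a restated rule. Survival follow-up (section 3.5) and on-treatment examination and medication records (section 10.2) already exist. A few extra scans may be needed, depending on item 6. The estimate may be lower, censoring widens its interval, and censoring assumes that the other missing scans are unrelated to CNS outcome. If missing-as-failure were made primary instead, 10% and 20% outcome-neutral loss would cut the effective rate from 35% to 31.5% and 28%, and the power of 8/20 from 39.9% to 27.5% and 17.1%.
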